14.3.4 Other Safety Data Summary Tables

Table 14.3.4.1	SAFETY	Summary of Vital Signs by Visit
Table 14.3.4.2	SAFETY	Summary of Electrocardiogram (ECG) Assessment by Visit
Table 14.3.4.3	SAFETY	Summary of Electrocardiogram (ECG) Data by Visit
Table 14.3.4.4	SAFETY	Electrocardiogram (ECG) Data: Shift in Assessments Compared to Baseline
Table 14.3.4.5	SAFETY	Summary of Bone Age
Table 14.3.4.6	SAFETY	Physical Examination Results by Body System and Visit
Table 14.3.4.7	SAFETY	Pubertal Status: Summary Assessment by Sex and Visit
Table 14.3.4.8.1	SAFETY	Local Tolerability from Site by Visit: Summary of Subjects with Injection Related Events
Table 14.3.4.8.2	SAFETY	Local Tolerability from Site by Visit and Severity: Summary of Subjects with Injection Related Events
Table 14.3.4.8.3	SAFETY	Local Tolerability from Site by Maximum Severity and Symptom for Overall Study: Summary of Subjects with Injection Related Events
Table 14.3.4.8.4.1	SAFETY	Local Tolerability from Patient Diary by Week - TransCon hGH: Summary of Subjects with Injection Related Events
Table 14.3.4.8.4.2	SAFETY	Local Tolerability from Patient Diary by Day - Genotropin: Summary of Subjects with Injection Related Events
Table 14.3.4.8.5.1	SAFETY	Local Tolerability from Patient Diary by Week and Severity - TransCon hGH: Summary of Subjects with Injection Related Events
Table 14.3.4.8.5.2	SAFETY	Local Tolerability from Patient Diary by Day and Severity - Genotropin: Summary of Subjects with Injection Related Events
Table 14.3.4.8.6	SAFETY	Local Tolerability from Patient Diary by Maximum Severity and Symptom for Overall Study: Summary of Subjects with Injection Related Events
Table 14.3.4.8.7	SAFETY	Exposure Adjusted Local Tolerability from Patient Diary for Overall Study
Table 14.3.4.8.8	SAFETY	Exposure Adjusted Local Tolerability from Patient Diary by Severity for Overall Study
Table 14.3.4.9	SAFETY	Concomitant Medication: Incidences by ATC Level 2 and 4
Table 14.3.4.10.1	SAFETY	Exposure to Study Treatment and Compliance
Table 14.3.4.10.2.1	SAFETY	Exposure to Study Treatment by Week – TransCon hGH
Table 14.3.4.10.2.2	SAFETY	Exposure to Study Treatment by Day – Genotropin
Table 14.3.4.10.3	SAFETY	Summary of Dose Timings
Table 14.3.4.10.4	SAFETY	Weight-based Planned Dosage (mg/dose) by Visit
Table 14.3.4.11	SAFETY	Serum concentration by Visit and PK analytes
Table 14.3.4.12	PK	Serum Concentration by Time Point and PK analytes at Visit: Individual data including Summary Statistics

Table 14.3.4.13	PK	PK Analysis at Visit 3: Individual PK Parameters including Summary Statistics
Table 14.3.4.14.1	PD	Serum Concentration / SDS by PD analyte and Time Point at Visit 3: Individual Data Including Summary Statistics (Absolute)
Table 14.3.4.14.2	PD	Serum Concentration / SDS by PD analyte and Time Point at Visit 3: Individual Data Including Summary Statistics (Baseline-Corrected)
Table 14.3.4.15.1	PD	PD Analysis at Visit 3; Individual PD Parameters Including Summary Statistics (Absolute)
Table 14.3.4.15.2	PD	PD Analysis at Visit 3; Individual PD Parameters Including Summary Statistics (Baseline-Corrected)

13.4 FIGURES

Figure 1	ITT	Annualized HV (LS Mean \pm SE) at Visit 6 (Week 52) for weekly TransCon hGH and daily hGH treatment groups
Figure 2	ITT	Distribution of Annualized HV at Week 52 for weekly TransCon hGH and daily hGH treatment groups
Figure 3	ITT	Annualized HV (Mean \pm SE) over 52 weeks for the TransCon hGH and the daily hGH treatment groups
Figure 4	ITT	Distribution of Annualized HV over 52 weeks for weekly TransCon hGH and daily hGH treatment groups
Figure 5	ITT	Delta Height SDS (LS Mean \pm SE) at Week 52 for weekly TransCon hGH and daily hGH treatment groups
Figure 6	ITT	Distribution of delta height SDS at Week 52 for weekly TransCon hGH and daily hGH treatment groups
Figure 7	ITT	Delta Height SDS (Mean \pm SE) over 52 weeks for the TransCon hGH and the daily hGH treatment groups
Figure 8	ITT	Distribution of delta Height SDS over 52 weeks for weekly TransCon hGH and daily hGH treatment groups
Figure 9	ITT	Height SDS (Mean \pm SE) over 52 weeks for weekly TransCon hGH and daily hGH treatment groups
Figure 10	ITT	Distribution of Height SDS over 52 weeks for weekly TransCon hGH and daily hGH treatment groups
Figure 11	ITT	Distribution of Height Velocity SDS over 52 weeks for weekly TransCon hGH and daily hGH treatment groups
Figure 12	ITT	Serum IGF-1 SDS (LS Mean \pm SE) over 52 weeks for weekly TransCon hGH and daily hGH treatment groups
Figure 13	ITT	Distribution of IGF-1 SDS over 52 weeks for weekly TransCon hGH and daily hGH treatment groups
Figure 14	ITT	Proportion of patients with normalized serum IGF-1 (0 – (+2.0) SDS) based on the average IGF-1 SDS at steady states for the TransCon hGH and the daily hGH treatment groups
Figure 15	ITT	Proportion of patients with normalized serum IGF-1 (0 – (+2.0) SDS) over 52 weeks for the TransCon hGH and the daily hGH treatment groups

- Figure 16 ITT Serum IGFBP-3 SDS (Mean \pm SE) over 52 weeks for weekly TransCon hGH and daily hGH treatment groups
- Figure 17 ITT Distribution of IGFBP-3 SDS over 52 weeks for weekly TransCon hGH and daily hGH treatment groups
- Figure 18 ITT Proportion of patients with normalized serum IGF-1 (-2.0 – (+2.0) SDS) over 52 weeks for the TransCon hGH and the daily hGH treatment groups
- Figure 19 ITT Proportion of patients with IGF-1 between -1.0 – (+2.0) SDS over 52 weeks for the TransCon hGH and the daily hGH
- Figure 20 ITT Distribution of Serum Concentrations of TransCon PEG40 hGH (ng hGH/mL) over 52 weeks for weekly TransCon hGH treatment group
- Figure 21 ITT Distribution of IGF-1 over 52 weeks for weekly TransCon hGH and daily hGH treatment groups
- Figure 22 ITT Difference Between Chronological Age and Bone Age at baseline versus Difference Between Increase in Bone Age and Increase in Chronological Age by Treatment
- Figure 23.1 PK/PD Mean (+SE) Serum Concentrations of TransCon hGH versus Time at Visit 3 (Linear Scale)
- Figure 23.2 PK/PD Mean (+SE) Serum Concentrations of hGH versus Time at Visit 3 (Linear Scale)
- Figure 23.3 PK/PD Mean (+SE) Serum Concentrations of mPEG versus Time at Visit 3 (Linear Scale)
- Figure 24.1 PK/PD Mean (+SE) Serum Concentrations of TransCon hGH versus Time at Visit 3 (Semi-Logarithmic Scale)
- Figure 24.2 PK/PD Mean (+SE) Serum Concentrations of hGH versus Time at Visit 3 (Semi-Logarithmic Scale)
- Figure 24.3 PK/PD Mean (+SE) Serum Concentrations of mPEG versus Time at Visit 3 (Semi-Logarithmic Scale)
- Figure 25.1 PK/PD Spaghetti Plots of Individual Serum Concentrations of TransCon hGH versus Time at Visit 3 (Linear Scale)
- Figure 25.2 PK/PD Spaghetti Plots of Individual Serum Concentrations of hGH versus Time at Visit 3 (Linear Scale)
- Figure 25.3 PK/PD Spaghetti Plots of Individual Serum Concentrations of mPEG versus Time at Visit 3 (Linear Scale)
- Figure 26.1 PK/PD Spaghetti Plots of Individual Serum Concentrations of TransCon hGH versus Time at Visit 3 (Semi-Logarithmic Scale)
- Figure 26.2 PK/PD Spaghetti Plots of Individual Serum Concentrations of hGH versus Time at Visit 3 (Semi-Logarithmic Scale)
- Figure 26.3 PK/PD Spaghetti Plots of Individual Serum Concentrations of mPEG versus Time at Visit 3 (Semi-Logarithmic Scale)
- Figure 27.1 PK/PD Mean (+SE) Serum Concentrations of IGF-1 (Absolute) versus Time at Visit 3 (Linear Scale)
- Figure 27.2 PK/PD Mean (+SE) Serum Concentrations of IGFBP-3 (Absolute) versus Time at Visit 3 (Linear Scale)
- Figure 28.1 PK/PD Mean (+SE) Serum Concentrations of IGF-1 (Absolute) versus Time at Visit 3 (Semi-Logarithmic Scale)

- Figure 28.2 PK/PD Mean (+SE) Serum Concentrations of IGFBP-3 (Absolute) versus Time at Visit 3 (Semi-Logarithmic Scale)
- Figure 29.1 PK/PD Mean (+SE) Serum Concentrations of IGF-1 (Baseline-corrected) versus Time at Visit 3 (Linear Scale)
- Figure 29.2 PK/PD Mean (+SE) Serum Concentrations of IGFBP-3 (Baseline-corrected) versus Time at Visit 3 Linear Scale)
- Figure 30.1 PK/PD Mean (+SE) Serum Concentrations of IGF-1 (Baseline-corrected) versus Time at Visit 3 (Semi-Logarithmic Scale)
- Figure 30.2 PK/PD Mean (+SE) Serum Concentrations of IGFBP-3 (Baseline-corrected) versus Time at Visit 3 (Semi-Logarithmic Scale)
- Figure 31.1 PK/PD Mean (+SE) IGF-1 SD-Scores (Absolute) versus Time at Visit 3 (Linear Scale)
- Figure 31.2 PK/PD Mean (+SE) IGFBP-3 SD-Scores (Absolute) versus Time at Visit 3 (Linear Scale)
- Figure 32.1 PK/PD Mean (+SE) IGF-1 SD-Scores (Absolute) versus Time at Visit 3 (Semi-Logarithmic Scale)
- Figure 32.2 PK/PD Mean (+SE) IGFBP-3 SD-Scores (Absolute) versus Time at Visit 3 (Semi-Logarithmic Scale)
- Figure 33.1 PK/PD Mean (+SE) IGF-1 SD-Scores (Baseline-corrected) versus Time at Visit 3 (Linear Scale)
- Figure 33.2 PK/PD Mean (+SE) IGFBP-3 SD-Scores (Baseline-corrected) versus Time at Visit 3 Linear Scale)
- Figure 34.1 PK/PD Mean (+SE) IGF-1 SD-Scores (Baseline-corrected) versus Time at Visit 3 (Semi-Logarithmic Scale)
- Figure 34.2 PK/PD Mean (+SE) IGFBP-3 SD-Scores (Baseline-corrected) versus Time at Visit 3 (Semi-Logarithmic Scale)
- Figure 35.1 PK/PD Spaghetti Plots of Individual Serum Concentrations of IGF-1 (Absolute) versus Time at Visit 3 (Linear Scale)
- Figure 35.2 PK/PD Spaghetti Plots of Individual Serum Concentrations of IGFBP-3 (Absolute) versus Time at Visit 3 (Linear Scale)
- Figure 36.1 PK/PD Spaghetti Plots of Individual Serum Concentrations of IGF-1 (Absolute) versus Time at Visit 3 (Semi-Logarithmic Scale)
- Figure 36.2 PK/PD Spaghetti Plots of Individual Serum Concentrations of IGFBP-3 (Absolute) versus Time at Visit 3 (Semi-Logarithmic Scale)
- Figure 37.1 PK/PD Spaghetti Plots of Individual Serum Concentrations of IGF-1 (Baseline-corrected) versus Time at Visit 3 (Linear Scale)
- Figure 37.2 PK/PD Spaghetti Plots of Individual Serum Concentrations of IGFBP-3 (Baseline-corrected) versus Time at Visit 3 (Linear Scale)
- Figure 38.1 PK/PD Spaghetti Plots of Individual Serum Concentrations of IGF-1 (Baseline-corrected) versus Time at Visit 3 (Semi-Logarithmic Scale)
- Figure 38.2 PK/PD Spaghetti Plots of Individual Serum Concentrations of IGFBP-3 (Baseline-corrected) versus Time at Visit 3 (Semi-Logarithmic Scale)
- Figure 39.1 PK/PD Spaghetti Plots of Individual IGF-1 SD-Scores (Absolute) versus Time at Visit 3 (Linear Scale)

- Figure 39.2 PK/PD Spaghetti Plots of Individual IGFBP-3 SD-Scores (Absolute) versus Time at Visit 3 (Linear Scale)
- Figure 40.1 PK/PD Spaghetti Plots of Individual IGF-1 SD-Scores (Absolute) versus Time at Visit 3 (Semi-Logarithmic Scale)
- Figure 40.2 PK/PD Spaghetti Plots of Individual IGFBP-3 SD-Scores (Absolute) versus Time at Visit 3 (Semi-Logarithmic Scale)
- Figure 41.1 PK/PD Spaghetti Plots of Individual IGF-1 SD-Scores (Baseline-corrected) versus Time at Visit 3 (Linear Scale)
- Figure 41.2 PK/PD Spaghetti Plots of Individual IGFBP-3 SD-Scores (Baseline-corrected) versus Time at Visit 3 (Linear Scale)
- Figure 42.1 PK/PD Spaghetti Plots of Individual IGF-1 SD-Scores (Baseline-corrected) versus Time at Visit 3 (Semi-Logarithmic Scale)
- Figure 42.2 PK/PD Spaghetti Plots of Individual IGFBP-3 SD-Scores (Baseline-corrected) versus Time at Visit 3 (Semi-Logarithmic Scale)
- Figure 43 SAFETY Glucose Levels (mg/dL) (Mean \pm SE) over 52 weeks for the TransCon hGH and the daily hGH treatment groups
- Figure 44 SAFETY HbA1c Levels (%) (Mean \pm SE) over 52 weeks for the TransCon hGH and the daily hGH treatment groups
- Figure 45 SAFETY Glucose Levels (mmol/L) (Mean \pm SE) over 52 weeks for the TransCon hGH and the daily hGH treatment groups
- Figure 46 SAFETY FT4 Levels (ng/dL) (Mean \pm SE) over 52 weeks for the TransCon hGH and the daily hGH treatment groups
- Figure 47 SAFETY Cortisol Levels (ug/dL) (Mean \pm SE) over 52 weeks for the TransCon hGH and the daily hGH treatment groups
- Figure 48 SAFETY FT4 Levels (pmol/L) (Mean \pm SE) over 52 weeks for the TransCon hGH and the daily hGH treatment groups
- Figure 49 SAFETY Cortisol Levels (nmol/L) (Mean \pm SE) over 52 weeks for the TransCon hGH and the daily hGH treatment groups
- Figure 50.1 SAFETY Shift in Glucose Levels (mg/dL) from baseline to Week 5 for the TransCon hGH and the daily hGH treatment groups
- Figure 50.2 SAFETY Shift in Glucose Levels (mg/dL) from baseline to Week 26 for the TransCon hGH and the daily hGH treatment groups
- Figure 50.3 SAFETY Shift in Glucose Levels (mg/dL) from baseline to Week 52 for the TransCon hGH and the daily hGH treatment groups
- Figure 51.1 SAFETY Shift in HbA1c Levels (%) from baseline to Week 5 for the TransCon hGH and the daily hGH treatment groups
- Figure 51.2 SAFETY Shift in HbA1c Levels (%) from baseline to Week 13 for the TransCon hGH and the daily hGH treatment groups
- Figure 51.3 SAFETY Shift in HbA1c Levels (%) from baseline to Week 26 for the TransCon hGH and the daily hGH treatment groups
- Figure 51.4 SAFETY Shift in HbA1c Levels (%) from baseline to Week 39 for the TransCon hGH and the daily hGH treatment groups
- Figure 51.5 SAFETY Shift in HbA1c Levels (%) from baseline to Week 52 for the TransCon hGH and the daily hGH treatment groups

- Figure 52.1 SAFETY Shift in Glucose Levels (mmol/L) from baseline to Week 5 for the TransCon hGH and the daily hGH treatment groups
- Figure 52.2 SAFETY Shift in Glucose Levels (mmol/L) from baseline to Week 26 for the TransCon hGH and the daily hGH treatment groups
- Figure 52.3 SAFETY Shift in Glucose Levels (mmol/L) from baseline to Week 52 for the TransCon hGH and the daily hGH treatment groups
- Figure 53.1 SAFETY Shift in FT4 Levels (ng/dL) from baseline to Week 13 for the TransCon hGH and the daily hGH treatment groups
- Figure 53.2 SAFETY Shift in FT4 Levels (ng/dL) from baseline to Week 26 for the TransCon hGH and the daily hGH treatment groups
- Figure 53.3 SAFETY Shift in FT4 Levels (ng/dL) from baseline to Week 52 for the TransCon hGH and the daily hGH treatment groups
- Figure 54.1 SAFETY Shift in Cortisol Levels (ug/dL) from baseline to Week 13 for the TransCon hGH and the daily hGH treatment groups
- Figure 54.2 SAFETY Shift in Cortisol Levels (ug/dL) from baseline to Week 26 for the TransCon hGH and the daily hGH treatment groups
- Figure 54.3 SAFETY Shift in Cortisol Levels (ug/dL) from baseline to Week 52 for the TransCon hGH and the daily hGH treatment groups
- Figure 55.1 SAFETY Shift in FT4 Levels (pmol/L) from baseline to Week 13 for the TransCon hGH and the daily hGH treatment groups
- Figure 55.2 SAFETY Shift in FT4 Levels (pmol/L) from baseline to Week 26 for the TransCon hGH and the daily hGH treatment groups
- Figure 55.3 SAFETY Shift in FT4 Levels (pmol/L) from baseline to Week 52 for the TransCon hGH and the daily hGH treatment groups
- Figure 56.1 SAFETY Shift in Cortisol Levels (nmol/L) from baseline to Week 13 for the TransCon hGH and the daily hGH treatment groups
- Figure 56.2 SAFETY Shift in Cortisol Levels (nmol/L) from baseline to Week 26 for the TransCon hGH and the daily hGH treatment groups
- Figure 56.3 SAFETY Shift in Cortisol Levels (nmol/L) from baseline to Week 52 for the TransCon hGH and the daily hGH treatment groups

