--	---

	
administration for Cohort 1 and the day after the last Genotropin administration in Cohort 2.
 
It is suggested that the site staff follows up with the subject between the visits by eg, phone calls.
 
Safety and efficacy assessments will be performed throughout the trial. All samples obtained after Informed Consent will be shipped to a selected central laboratory for analysis. Safety samples may be analyzed locally in case of emergency or if logistics or other unforeseen events do not permit a central analysis. During visits where study drug administration is planned at the site, these assessments will be performed prior to such administration (predose). While fasting is recommended for all visits, fasting is required at Visits 1, 4, and 6. The following procedures will be performed during V1 through V6 unless otherwise indicated:
 
1) Physical examination and vital sign measurement (blood pressure, heart rate, body temperature, respiratory rate) (subjects should rest for at least 5 minutes before vital sign assessment)2) Review of concomitant medication3) Review of Subject Diary by investigator (V2-V6)4) Evaluation of Adverse Events (AEs) and local tolerability5) Safety assessments:
• Hormone levels {TSH, fT4, fT3, and morning cortisol; V1 (fasting), V3, V4 (fasting) and V6 (fasting)}• Routine safety biochemistry parameters (sodium, potassium, calcium, phosphate, chloride, total bilirubin, alkaline phosphatase, lactate dehydrogenase (LDH), aspartate aminotransferase (AST), alanine aminotransferase (ALT), gamma-glutamyl transferase (GGT), albumin, total protein, creatinine, urea-nitrogen, uric acid, serum iron and transferrin)• Hematology parameters (hemoglobin, leukocytes, differential blood count of leukocytes, platelet count; blood smears will be performed locally for back-up analysis, if needed)• Parameters of glucose metabolism: fasting glucose (when required), insulin, and HbA1c (glucose metabolism parameters can be assessed locally at any time if there is
--	---

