13.1.3 Safety Endpoints

- Incidence of AEs
- Local tolerability (assessed by the subject, the parents/legal guardians and the investigator)
- Incidence of anti-hGH antibodies including neutralizing antibodies as needed (both cohorts) and incidence of treatment-emergent anti-PEG antibody formation (in TransCon hGH subjects)

- IGF-1 levels and IGF-1 SDS
- Parameters of glucose metabolism (fasting glucose and insulin level, HbA1c) and lipid parameters
- Hormone levels: thyroid status and morning cortisol
- All other hematology and biochemistry blood parameters
- ECG
- Results of the physical examinations, vital sign measurements
- Bone age at 52 weeks

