6.1.1 Baseline Data

Baseline is defined as data collected at Visit 1. If data are missing at Visit 1, then data from screening will be used as baseline instead.

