9.2 Clinical Laboratory Evaluations

Descriptive summaries of actual (absolute) values and changes from baseline values if applicable will be presented for the following by treatment and visit in both original and standard units for the Safety Population using central laboratories data:

- Biochemistry: sodium, potassium, calcium, phosphate, chloride, total bilirubin, alkaline phosphatase, lactate dehydrogenase (LDH), aspartate aminotransferase (AST), alanine aminotransferase (ALT), gamma glutamyl transferase (GGT), albumin, total protein, creatinine, urea nitrogen, uric acid, serum iron and transferrin
- Hematology: hemoglobin, leukocytes, differential blood count of leukocytes, platelet count
- Hormone Levels: thyroid status (TSH, fT4, and fT3 levels) and morning cortisol
- Glucose Metabolism: HbA1c, and fasting insulin and glucose, HbA1c.
- Lipid Metabolism: Total cholesterol, triglycerides, HDL and LDL

Laboratory values will be displayed in the data listings and those that are outside the normal range will be flagged, along with corresponding normal ranges. Any out-of-range values that are identified by the investigator as being clinically significant will be presented in a data listing. For each laboratory parameter, if applicable, shifts in assessments of abnormality from baseline to each post-baseline visit will be presented (shift tables) for data from central laboratories.

Data listings of laboratory will also be provided, displaying details of each laboratory test captured on the CRF for central and local laboratories separately.

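### Fasting glucose and insulin displays can mix fasted baseline values with values from visits where fasting is only recommended (Week 5 in the shift figures)

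*SAP*

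**What the plan says.** Protocol 13.1.3 lists among the safety endpoints "Parameters of glucose metabolism (fasting glucose and insulin level, HbA1c) and lipid parameters", and SAP 2.2.2 repeats it. SAP 9.2 describes the glucose-metabolism panel as "HbA1c, and fasting insulin and glucose, HbA1c", to be summarised by treatment and visit, with shift tables from baseline to each post-baseline visit.

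The fasting rule is in the Protocol synopsis and again in section 10.3.1: "While fasting is recommended for all visits, fasting is required at Visits 1, 4, and 6". The Schedules of Events (17.2 and 17.3) mark fasting as required at Screening, V1, V4 and V6 only, while safety laboratory samples are taken at every visit. Section 10.1.2 qualifies the glucose item in the same way: it is a fasting measurement where fasting is required.

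On baseline, SAP 6.1.1 says "Baseline is defined as data collected at Visit 1" and "If data are missing at Visit 1, then data from screening will be used as baseline instead". Both possible sources are therefore required-fasting visits.

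SAP 13.4 plans Figure 50.1, "Shift in Glucose Levels (mg/dL) from baseline to Week 5 for the TransCon hGH and the daily hGH treatment groups", and Figure 52.1, "Shift in Glucose Levels (mmol/L) from baseline to Week 5 for the TransCon hGH and the daily hGH treatment groups". Companion figures cover Weeks 26 and 52. Figures 43 and 45 show mean glucose over 52 weeks, and their titles name neither visits nor fasting state.

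**The concern.** Glucose and insulin depend on recent food intake. If baseline is fasted and some later samples are not, the change from baseline includes a meal effect as well as any drug effect. Figures 50.1 and 52.1 are the only glucose shift figures before Week 26, so a reader looking for an early effect of growth hormone on glucose could not tell the two apart. The same applies to the Week 5, 13 and 39 rows of the by-visit glucose and insulin tables.

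The distortion need not be equal in the two arms. Visit 2 is a predose visit on a dosing day for TransCon hGH but falls on any day of Week 5 for Genotropin. Protocol 10.1 puts all visits in the morning, yet the cohort text is firmer for TransCon hGH (10.1.2.1) than for Genotropin (10.1.2.2), where morning is a preference at visits that do not require fasting. The trial is open-label, so adherence to a recommendation could differ by arm.

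**Working it through.** The plan states no figure for this point, so there is nothing to reproduce. The check sets the planned glucose figures against the fasting schedule.

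**Step 1. Weeks against fasting status** (Protocol 17.2 and 17.3; SAP 13.4)

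| Week | Visit | Fasting | Glucose shift figures | HbA1c shift figure |
|---|---|---|---|---|
| 5 | V2 | recommended | 50.1, 52.1 | 51.1 |
| 13 | V3 | recommended | none | 51.2 |
| 26 | V4 | required | 50.2, 52.2 | 51.3 |
| 39 | V5 | recommended | none | 51.4 |
| 52 | V6 | required | 50.3, 52.3 | 51.5 |

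The glucose shift figures cover Weeks 5, 26 and 52. Required-fasting weeks after baseline are 26 and 52. The mismatch is Week 5 alone, in Figures 50.1 and 52.1. Figures 50.2, 50.3, 52.2 and 52.3 compare like with like.

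**Step 2. Neighbouring figures.** HbA1c, which does not depend on fasting, is plotted at all five weeks. Free T4 shifts (Figures 53.1 to 53.3) are at Weeks 13, 26 and 52, exactly the post-baseline visits at which hormones are sampled. Glucose omits Weeks 13 and 39 but keeps Week 5, which has the same fasting status. That suggests an oversight but does not prove one.

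**Step 3. Unscheduled samples.** SAP 6.1.3, Table 3, maps unscheduled and early-termination visits to the nearest scheduled visit: Days 2 to 58 to Week 5, Days 134 to 224 to Week 26, Day 318 onward to Week 52. No fasting condition is stated, so a sample of unknown fasting state could also supply a Week 26 or Week 52 value.

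**Step 4. Size.** Let *f* be the share of Week 5 samples that are unfasted and *d* the mean rise in glucose in those samples. The bias in the mean shift is *f* × *d*. The documents give neither, so both are assumed:

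- *f* from 0.1 to 0.5 and *d* from 5 to 20 mg/dL: 0.1 × 5 = 0.5 to 0.5 × 20 = 10 mg/dL.
- *f* from 0.2 to 0.4 and *d* from 15 to 30 mg/dL: 0.2 × 15 = 3 to 0.4 × 30 = 12 mg/dL.

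The two sets together span 0.5 to 12 mg/dL.

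The bias in the between-arm difference is the difference in *f* between arms times *d*. For a difference of 0.1 to 0.3 and *d* from 5 to 20 mg/dL, it runs from 0.1 × 5 = 0.5 to 0.3 × 20 = 6 mg/dL. With equal *f* and equal *d* in both arms it is zero.

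**The case against.** Fasting is recommended at every visit and visits are planned for the morning, so many Week 5 samples may be fasted. SAP 9.2 names the parameter as fasting, and one fair reading is that only fasted samples feed these outputs. The table shells are a separate document (SAP section 14), and a filter or footnote could be there. Week 5 may have been chosen deliberately as an early safety look. The displays are descriptive, both arms get the same recommendation, and HbA1c gives an early glycaemic display that is free of the problem.

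Most of this stands, and it limits the point. A reader might infer that the Week 5 values *are* non-fasting; the documents show only that they *can be*. Figures 43 and 45 are affected only if they plot V2, V3 or V5, which their titles leave open. What does not answer the point is the hope of an unseen filter. The SAP orders by-visit summaries and shift tables for glucose and insulin, and neither document says that fasting status is recorded per sample or how an unfasted value is to be handled.

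**Conclusion.** The point holds, as a minor one. Figures 50.1 and 52.1, the by-visit glucose and insulin summaries and shift tables under SAP 9.2, and possibly Figures 43 and 45, set a required-fasting baseline against visits where fasting is only recommended. A fasting safety endpoint can therefore be mixed with non-fasting values. The range of 0.5 to 12 mg/dL illustrates a formula under assumed inputs and does not estimate what will happen in this trial. No inferential test rests on these displays, and the primary height-velocity analysis is untouched.

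Three stronger readings are tempting but unsupported:

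- A reader might infer that many children would appear to cross the protocol's 100 mg/dL fasting-glucose level. No glucose distribution is given, so no crossing rate can be calculated.
- A reader might infer that dose decisions would be distorted. Protocol 9.6 ties those decisions to a child's own values and repeat tests, and these group figures play no part.
- A reader might extend the point to triglycerides. Neither document defines a fasting lipid endpoint.

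**What to change.** In SAP 9.2 and 13.4:

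- Restrict the fasting glucose and insulin summaries, shift tables and figures to Visits 1, 4 and 6 (with Screening as the baseline fallback). If fasting status is recorded, restrict them to samples confirmed as fasted instead.
- Apply the same condition to unscheduled and early-termination samples mapped by Table 3.
- Show Week 5, 13 and 39 values separately, labelled *fasting recommended, not required*. Deleting the Week 5 look would go further than needed.
- State in Figures 43 and 45 which visits are plotted.
- Leave the HbA1c displays as planned.

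The cost is a change of SAP wording and some reprogramming. The visit-based option needs no new data. The fasting displays will have fewer time points, but no value is lost, because the others remain in the separate display.
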